1 BACKGROUND

Instead of patients needing to speak to the receptionist, it has now become commonplace for general practice waiting rooms to host an automated check-in screen. Practice waiting rooms typically display a notice, directing patients arriving for a booked appointment, to self-check-in. In a time where primary care is underfunded¹, self-check-in is a cost effective process which frees up receptionist time for other tasks². Whilst this automated process provides an efficient solution to the completion of a practice administrative function, it may also be possible to quickly collect additional information about the consulting patient. There is little evidence available in the literature to describe the use of automated check-in screens for the collection of additional patient data and therefore an assessment of patient acceptability for providing additional information for the purposes of research, whilst self-completing an automated check-in screen is to be piloted.

In order to support the delivery of health and social care, the role of technology enabled care services (TECS) are gaining increasing recognition³. We can provide parallels in how people have converted to using technology in their everyday lives, for example in banking, shopping and communications, with how people receive delivery of health and social care⁴. The use of TECS support the transformation of new models of care delivery and allow patients to meet their needs and preferences, together with the provision of efficiencies for general practice. Improving digital literacy across the health and social care landscape needs to be embedded in organisations and individuals⁵. An automated check-in screen which displays additional health related questions is also one way of providing patients with the ability to take control of their choices and how their personal data are managed.

The EU General Data Protection Regulation (GDPR) replaced the Data Protection Directive 95/46/EC on 25th May 2018. As part of this new regulation there is the right of the data subject to obtain from the data controller, confirmation as to whether or not personal data concerning them is being processed, where and for what purpose⁶. General practices are data controllers, of patients' (data subjects) healthcare data. This new legislation allows data subjects to have control over how their data is processed by the controller. The invitation to participate in healthcare research and the percentage conversion rate into participants recruited is variable, with many comprehensible and confounding factors affecting recruitment success rates. Collecting data on whether patients are happy to be contacted about research would provide general practices with efficiencies in resource, improved accuracy in sampling and provide patients with more control of how their data are used.

Increasingly, patients are living with multiple, long-term chronic conditions, both physical and psychological - and at the same time general practitioners are being asked to do more routine health checks, ask more questions and give more advice as standard during consultations. The standard 10-minute appointment is simply inadequate to deal with this⁷. Pain is commonly neglected by patients and not prioritised by general practitioners. Although effective pain management interventions and

programmes exist, provision of these services is inconsistent, and chronic pain is not given the priority it requires in view of the extent of its burden on individuals and society⁸. There being a prompt for patients to complete at checking in for a booked consultation at the general practice, with regards to the patient's recent experiences of pain, might then encourage them to highlight this in a consultation. This data collected can additionally be entered straight into the patient's medical record and can facilitate the impending consultation, making an efficient use of the 10-minute consultation.

The electronic Clinical Record Management system which each general practice uses, is dictated by their local Clinical Commissioning Group (CCG). The general practice systems of choice (GPSoC) are EMIS Health, TPP SystmOne, Vision, and Microtest Health. These systems are used by 56%, 36%, 7% and 1% respectively, of general practices within England⁹. These GPSoC are now designed to include optional extras for general practices; patients can be provided with information, provide feedback for service evaluation and book future appointments using the interoperability functions of these systems¹⁰. Some have a questionnaire module, which can be used to gain responses from specific patient groups in order to improve services or collect Quality and Outcomes Framework (QOF) data. In addition, all of these systems now integrate with automated check-in screens. Patients can notify the general practice of their arrival for a consultation more efficiently. A few presses on a touch screen kiosk updates the GPSoC of the patient's arrival for their consultation and the patient receives confirmation of their appointment in seconds, without administration staff having to take any action.

EMIS is the clinical system of choice used by 67% of practices across the NIHR Clinical Research Network: West Midlands (CRN WM) and the customisable options it offers, provides us with an opportunity to pilot its use in the collection of additional, brief research data from consulting patients.

2 AIM & OBJECTIVES

The aim of this study is to examine patient acceptability, for providing brief research information, whilst self-completing an automated check-in screen prior to any general practice consultation.

Primary objective

The specific objectives of this study fall into two categories; research evaluation and process evaluation. By piloting the use of the automated check-in screen to collect additional research data, the answers to these objectives will then provide feasibility information on the future use of the automated check-in screens for the identification of potentially eligible participants that would be happy to be contacted about future research studies relevant to their health and with information on patient acceptability of answering simple research questions, within the general practice waiting room.

Research evaluation objectives:

1. To examine completion rates of the two additional research questions on the automated check-in screen.
2. To estimate the number of patients that would be happy to be contacted about future research studies relevant to their health.
3. To estimate the number of patients reporting degrees of pain and which severities of pain.
4. To explore any demographic variances in completion responses.
5. To estimate research question completion rate feasibility, for future use of automated check-in screens in the collection of research data.

Process evaluation objectives;

1. To assess patient acceptability of answering an additional two research questions within the waiting room, whilst completing an automated check-in screen.
2. To explore research question completion rates depending on the time differences between; check-in completion, booked appointment time and actual consultation time.
3. To assess the impact of check-in completion for general practice operationalisation.
4. To describe the quantity and detail of any participant queries, made as a result of asking two additional research questions on the patient automated check-in screen.

3 STUDY DESIGN

This pilot feasibility study will examine patient acceptability of completing two research questions following automated check-in, within participating general practices.

Ethical approval will be sought for the collection and analysis of the additional two pieces of research data collected at the point of automated check-in by the patient, together with associated simple operational and demographic data. In line with the definition outlined in Article 4(11) of the GDPR guidance, “any freely given, specific, informed and unambiguous indication of the data subject’s wishes by which he or she, by a statement or by a clear affirmative action, signifies agreement to the processing of personal data relating to him or her”⁶, participants will be recruited to this study. Consent to participate will be implied by question completion. An invitation poster will be displayed next to the automated check-in screen providing general information on the study, together with participant information leaflets

providing details on how any affirmative action made can be changed and will also contain contact details for the AC DC study team, should the patient wish to ask any questions about the study.

3.1 Study population

All patients of age 18 and over, who can read and respond in English and with a booked appointment, consulting with any Health Care Professional (HCP) at their general practice, during the recruitment period will be eligible to participate. All patients are required to confirm their attendance at the general practice by using the automated check-in screen. If the patient completing the automated check-in screen is 18 years of age or over, the additional research questions will appear for completion. The additional research questions will not appear on any subsequent appointment check-in screen during the recruitment period, for those participants who have already completed the questions.

3.1.1 Eligibility

Inclusion criteria

- Patients 18 years of age or over attending participating general practices for a consultation with any healthcare professional.
- Patients registered with the participating general practice during the specified recruitment period.
- Patients able to read and respond in English.

Exclusion criteria

- Patients under the age of 18 attending the general practice for a consultation with a healthcare professional.

4 STUDY SETTING

Selected general practices within NIHR Clinical Research Network: West Midlands (CRN WM) whose GPSoC is EMIS, will host the additional two research questions on their automated check-in screen, within the patient waiting room area, for a period of 3 weeks recruitment per practice. The general practice EMIS system will require Automated Arrival facilities, to include a Questionnaire Module and an automated arrivals check-in touchscreen. This will enable any answer to a displayed question to have a Read / SNOMED code applied directly into the patient record without the need for administrative input. The study Health Informatics Specialist will coordinate the installation of the required software in participating practices (where a Questionnaire Module is not already available) and programme the check-in function to provide the additional research questions.

The average list size of CRN WM general practices is 7,500 and the minimum required appointments required per week, per 1,000 patients is 72¹¹. This will provide the study team with enough data to understand patient acceptability of completing two research questions in the general practice waiting room following automated check-in, per practice.

5 STUDY PROCEDURES

5.1 Recruitment

Patients book appointments for consultations with multiple HCPs at their registered general practice by either telephoning the practice and booking an appointment, physically attending the practice and booking an appointment or by booking appointments using the practice on-line services (if available). The management and administration of this process at a general practice, is coordinated by the Practice Manager alongside the practice administration team. Once patients attend for their booked appointment, the automated check-in screen provides efficiencies for the practice administration team, as patients are empowered to self-check-in.

5.2 Patient identification

During the recruitment period for each participating practice, all patients 18 years of age or over and able to read and respond in English attending for a booked appointment and completing an automated check-in screen confirming their attendance will be eligible to participate in the study.

The study will be advertised at each participating general practice during the 3-week recruitment period. An invitation poster will be on display informing patients of the study and Participant Information Leaflets (PIL) will be available next to the automated check-in screen for patients to take away if they wish. The poster and PIL will provide general information on the study, together with contact details for the research study team should the patient wish to ask any questions about the study or clarify the research process before deciding whether or not to participate. The PIL will also contain information on how patients can withdraw any information provided for the study.

Following a patient using an automated check-in screen to confirm their attendance for a booked appointment by selecting the day of the month they were born, the month they were born and then the first letter of their surname (as standard), the additional research questions will appear for completion. Only once the research questions have either been answered, 'skipped' or sufficient time has elapsed without a response, will the check-in screen provide confirmation of the patient's attendance.

5.3 Screening

The two research questions will not appear for patients checking-in for a booked appointment who are under the age of 18 years or for those that have already answered the research questions during the recruitment period.

5.4 Research questions

Following entry of the standard identification items, to confirm attendance for a booked appointment, a patient will be presented with the first research question for completion. The first research question to appear on the check in screen will be;

“How much bodily pain have you had during the past 4 weeks?”

With options for completion of;

“None”, “Very mild”, “Mild”, “Moderate”, “Severe”, “Very severe”

or

“Skip question”

Once a response to the question has been selected, the second research question will appear;

“Would you be happy for your practice to contact you about any future research studies which are relevant to your health, to improve care for patients in the NHS?”

With options for completion of;

“Yes, I'd be happy for you to contact me about research of relevance to me”, “No, thank you”

or

“Skip question”

If the patient takes no further action once the first research question appears, the screen awaits a response and after sufficient time has elapsed without a response, the automated check-in screen will return to the ‘Home’ screen, after confirming checked-in attendance for the booked appointment. The second question will therefore not be displayed.

If the patient answers the first research question however takes no further action once the second research question appears, again the screen awaits a response and after sufficient time has elapsed without a response, the automated check-in screen will return to the ‘Home’ screen, after confirming checked-in attendance for the booked appointment.

5.5 Consent

Consent to participate in this study will be obtained, in line with the definition outlined in Article 4(11) of the GDPR guidance, “any freely given, specific, informed and unambiguous indication of the data subject’s wishes by which he or she, by a statement or by a clear affirmative action, signifies agreement to the processing of personal data relating to him or her”⁶. Consent to participate will therefore be implied by question completion. The study invitation poster and PIL (displayed alongside the automated check-in screen for the period of recruitment) will explain the purpose of the study, what is involved and what will happen to data that the participant supplies. No patient identifiable information will be collected. Completion of the research questions will be taken as consent to participate in the study.

5.6 Data collection

A pseudonymised data extraction, for all booked appointments scheduled and attended during the three-week recruitment period at each participating practice, for those patients of age 18 years or older, will be downloaded. Data to be included in the download will include; patient demographic data (gender and age), date and times (of patient check-in, booked appointment and consultation), check-in ID (system user / practice) and self-reported answers to the two research questions. These items will form the basis of the quantitative data collection, see Table 1 for data items and from where the quantitative data will be collected.

For each participating practice, metadata to include; practice list size, demographic data (gender and age), deprivation score and total number of practice based consultations booked over the three-week recruitment period, will also be collected at aggregate level.

Participant data provided in terms of check-in queries, made as a result of the two additional research questions on the patient automated check-in screen will be anonymously logged by practice administration staff, to assess the impact of check-in completion for general practice operationalisation. The log of queries will be populated for a total of 4 weeks. Three weeks, during recruitment to the study and for one week following the end of recruitment.

Automated check-in data collection

Patients will be asked to complete two self-report research questions during automated check-in for a booked appointment at their general practice. The data entered will be appended to their electronic medical record and pseudonymised data will be downloaded, for all patients for whom the research questions appeared. This data will consist of unique study identifiers, gender, age, times (check-in, booked and consultation), check-in ID (system user / practice) and the study research coded entries.

Table 1: Data items and method of data collection

Data items	Description	Method of data collection
Patient demographics	Gender	EMIS data extraction
	Age	
Date and time of:	Check-in	
	Booked appointment	
	Consultation	
Check-in ID	Dichotomous: 'System user' or 'Practice'	Patient self-reported
Degree of bodily pain experienced during the past 4 weeks.	Single question: 1-6 point scale – degree of pain	
Consent to contact about future research studies of relevance.	Dichotomous: Yes or No	

5.7 Long term use of data collected

Data collected on the degree of bodily pain experienced during the past 4 weeks will be retained at the general practice. The response provided as to whether the patient would be happy for their practice to contact them about any future research studies relevant to their health, will be a clinical coded entry retained in the patient's electronic medical record, unless the patient requests to amend their response or if processing operations or purposes evolve¹⁴.

5.8 Withdrawal criteria

Patients will be able to withdraw data provided for the study by either contacting a member of the AC DC study team or by informing practice administration staff of the amendment they would like to make to entered data. This therefore provides patients with up to a 4 week 'cooling off' period (before pseudonymised data is downloaded) should they wish to retract or amend their participation in the study.

Patients will be able to amend their response at any time in the future, to whether they are happy for their practice to contact them about any future research studies which are relevant to their health. To amend their response to this question they will need to inform the practice administration staff.

5.9 End of study

At each participating practice, recruitment will be ongoing for 21 consecutive days and a pseudonymised data extraction will be made for the 21-day recruitment period on or after day 28. The pseudonymised data extraction and meta data will be extracted by practice administration staff and securely transferred via nhs.net email to the Research Institute for Primary Care and Health Sciences (iPCHS). The study will last for 21 days at each participating general practice, after which time the additional two research questions will be removed from the automated check-in screen and the invitation poster and PILs removed from the general practice waiting room. The AC DC participant query log populated by general

practice administrative staff will be maintained for a period of 4 weeks at each participating general practice.

The end of the study is defined as the collection of data from the last participating practice. The HRA will be notified of the end of the study in accordance with Keele University SOPs.

6 STATISTICS AND DATA ANALYSIS

6.1 Sample size calculation

The average list size of CRN WM general practices is 7,500 patients, of which approximately 6,000 (80%) will be 18 years of age or over. With the minimum required appointments, per week, per 1,000 patients being 72¹¹. Assuming the same rate of appointment use in those under and over 18 years, there will be an average of 432 appointments per week for those aged 18 years of age or over. Over three weeks therefore, discounting an approximate 10% of patients who have either; >1 appointment booked within the three-week period, lack capacity to complete the automated check-in screen, or the appointment is for either a telephone appointment or a home visit, the practices can expect approximately 1166 eligible participants.

One of the outcomes of this study is to estimate the proportion of people who are happy for their practice to contact them about any future research studies which are relevant to their health. Assuming that approximately 50% will respond positively to this question, 9604 people will need to respond to the question in order to estimate a 95% confidence interval for this proportion formally with a precision of 0.01. Assuming that 80% of those who use the automated check-in complete the additional questions, this would require approximately 12005 people to complete an on-screen check-in in order to achieve sufficient responders. This equates to approximately 11 practices displaying the questions for 3 weeks each, dependent on practice size and actual use of the automated check-in screens.

One AC DC participant check-in query log per practice, completed by practice administration staff, with regards to queries made as a result of the two additional research questions on the patient automated check-in screen, will allow the study team to assess the impact of check-in completion for general practice operationalisation.

6.2 Statistical analysis plan

Simple descriptive statistics will be used to compare any demographic differences between responders and non-responders and to characterise the study sample. This is a descriptive study and we will determine frequencies and percentages of responses to the 2 questions, stratified by age, gender and practice. Mean or median times (as appropriate) between check-in, booked appointment and time of

consultation will be calculated in responders and non-responders separately. In the production of and reporting on subgroups, ONS guidance will be followed on statistical microdata, to ensure the confidentiality of individual persons is protected¹³.

Thematic content analysis will be used to interpret the participant data logged by practice administrative staff.

In accordance with Keele University SOPs, a Statistical Analysis Plan (SAP) will be completed prior to the end of recruitment.

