Chief Investigator	[name] Arthritis Research UK Primary Care Centre Research Institute for Primary Care & Health Sciences [name] [contact] [contact]
Principal Investigator	[name] Arthritis Research UK Primary Care Centre Research Institute for Primary Care & Health Sciences [name] [contact] [contact]
Sponsor	[name] Head of Research Integrity, Directorate of Engagement & Partnerships, [name] [name] [contact]
Funder	[name]: NIHR Research Professorship (NIHR-RP-2014-04-026)
Study Management	Arthritis Research UK Primary Care Centre Research Institute for Primary Care & Health Sciences [name] [name] [contact]
Lead Statistician	[name] Senior Research Fellow: Epidemiology and Applied Statistics Arthritis Research UK Primary Care Centre Research Institute for Primary Care & Health Sciences [name] [contact] [contact]
Key Protocol Contributors	
 - [name], GP Partner & NIHR Academic Clinical Lecturer in General Practice - [name], Health Informatics Specialist Arthritis Research UK Primary Care Centre Research Institute for Primary Care & Health Sciences [name] [contact]

STUDY SUMMARY

Study title	Automated Check-in Data Collection Study	
Internal ref. number (or short title)	AC DC STUDY	
Study design	Pilot feasibility	
Study participants	Patients consulting in general practice, completing an automated check-in screen prior to their consultation.	
Planned sample size	Approximately n=1166 per participating general practice (depending on practice list size and number of consulting clinicians during recruitment period). Total sample size n=9604, ~11 general practices	
Planned recruitment period	3 weeks in each participating general practice.	
	Objectives	Outcome measures
Primary	To assess patient acceptability of answering two research questions in the general practice waiting room using an automated check-in screen.	Percentage of completed automated check-in screens with entered research data.

STUDY FLOW CHART

Flow chart demonstrating recruitment of participants into the study.

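### The primary outcome is worded per check-in screen; it should be defined per patient shown the questions, with intervals that allow for clustering by practice

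*Combined protocol and SAP*

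**What the plan says.** **Unit.** The Study Summary gives the primary outcome measure as "Percentage of completed automated check-in screens with entered research data", so the unit is the screen. Section 6.1 counts people: 9604 responders, and 12005 people checking in on screen at an assumed 80% completion. Section 6.2 says "we will determine frequencies and percentages of responses to the 2 questions, stratified by age, gender and practice" and does not say whether the base is patients, appointments or screens. It defers a separate SAP, due before recruitment ends.

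**Who sees the questions.** Under section 3.1 they "will not appear on any subsequent appointment check-in screen during the recruitment period, for those participants who have already completed the questions". Section 5.3 withholds them "for those that have already answered the research questions during the recruitment period". Section 5.2 (the sentence starting "Only once the research questions have either been answered") lists answering, skipping and running out of time as three separate routes to a confirmed check-in. Section 5.4 includes Skip among the options for completing each question. It also says of a patient who does not react to question 1: "The second question will therefore not be displayed".

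**What is extracted.** Section 5.6 describes the download first as "A pseudonymised data extraction, for all booked appointments scheduled and attended during the three-week recruitment period", and later as covering the patients who were shown the questions. It includes unique study identifiers, age, gender, times and the coded answers.

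**The concern.** Whether a screen is displayed depends on the earlier response. A patient who answers drops out of later displays. A patient who times out can return within the three weeks and add another empty screen. Skippers may do the same, but the documents do not settle this: one section speaks of having completed the questions, another of having answered them, and Skip is treated once as a completion option and once as something other than answering.

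So non-responders can enter a per-screen denominator several times, while a patient who has fully answered supplies one screen with data. Read literally, the Study Summary's base is every completed check-in screen. It would then also score as failures the later visits at which responders were shown nothing.

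Completion is the study's headline measure of acceptability, and it could take different values from the same data depending on a denominator that nobody has fixed. The 0.01 precision in section 6.1 is a related matter: it treats patients from about 11 practices as one simple random sample, and section 6.2 mentions no allowance for practice.

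**Working it through.** **1. The plan's own figures reproduce.**
- Responders: 1.96² × 0.5 × 0.5 / 0.01² = 9604.
- On-screen check-ins: 9604 / 0.8 = 12005.
- Eligible per practice: 7500 × 0.8 × 72/1000 = 432 a week; 432 × 3 × 0.9 = 1166.4.
- Practices: 12005 / 1166 = 10.3, rounded up to 11.

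**2. Effect of the unit.** From section 6.1, take 80% completion at first showing. Assume that a share r of all patients check in a second time, that every non-responder who returns is shown the questions again, and that a share s of those answer then. Neither r nor s is in the documents. Section 6.1's 10% discount pools repeat bookers with lack of capacity, telephone appointments and home visits, which suggests r of at most about 10%; 20% is shown only to complete the range.
- Ever answered, per patient: P = 0.8 + 0.2rs
- Per screen that showed the questions: P / (1 + 0.2r)
- Per completed check-in screen: P / (1 + r)

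| r | s | Ever answered, per patient | Per screen shown | Per completed check-in screen |
|---|---|---|---|---|
| 5% | 0 | 80.0% | 0.8/1.01 = 79.2% | 0.8/1.05 = 76.2% |
| 10% | 0 | 80.0% | 0.8/1.02 = 78.4% | 0.8/1.10 = 72.7% |
| 20% | 0 | 80.0% | 0.8/1.04 = 76.9% | 0.8/1.20 = 66.7% |
| 10% | 0.8 | 81.6% | 0.816/1.02 = 80.0% | 0.816/1.10 = 74.2% |

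At r = 10% the gap from the ever-answered rate is 1.6 points per shown screen for both values of s, and 7.3 or 7.4 points per completed check-in screen.

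**3. The same rate against first presentation.** The per-shown-screen rate minus 0.8 equals 0.2r(s − 0.8)/(1 + 0.2r). At r = 10% this is −1.6 points for s = 0, zero for s = 0.8, and positive for larger s. Both size and direction depend on which patient-level rate is the target.

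**4. If skippers are not shown the questions again.** Suppose half of the non-responders skipped. Then only half can recur, and at r = 10%, s = 0 the per-shown-screen rate is 0.8/(1 + 0.2 × 0.5 × 0.1) = 79.2%. The figure per completed check-in screen does not change.

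**5. Sampling error and clustering.** Under simple random sampling the half-width for 80% completion is 1.96 × √(0.8 × 0.2/12005) = 0.72 points. The mean number per practice is 12005/11 = 1091. No intraclass correlation (ICC) is given, so 0.001, 0.005 and 0.01 are assumed. The design effect 1 + 1090 × ICC is 2.09, 6.45 and 11.9, and the half-width 0.72 × √(design effect) is 1.0, 1.8 and 2.5 points. For the contact question, 9604/11 = 873 responders per practice give 1 + 872 × ICC = 1.87, 5.36 and 9.72. The planned 1.0-point half-width becomes 1.4, 2.3 and 3.1 points.

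**The case against.** The best defence is that a sensible analyst would not use the literal base. Section 2 speaks of completion rates of the two questions, section 6.1 counts people and discounts repeat bookers, and one of the two descriptions in section 5.6 is by patient shown the questions. On that view the 72.7% figure rests on a strained reading, the realistic effect is 1.6 points or less, no completion threshold hangs on it, and the SAP still to be written can settle the denominator.

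Much of this stands. The effect is modest on the narrower base, and step 3 shows that it can vanish. At an assumed ICC of 0.005 or more it is also smaller than the clustered half-width. But the stated outcome is per screen, section 6.2 does not override it, and a promised SAP is where the repair belongs rather than evidence that it has been made.

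Three stronger readings are tempting and should not be drawn:
- That section 6.2 ignores non-responders. It compares their demographics with responders' and summarises check-in, booked and consultation times separately for each group. It does not use these data to adjust the pain and contact percentages.
- That the sample size is wrong. Every step follows from its inputs.
- That the unadjusted percentages are shown to be biased. The documents contain nothing on how non-responders would have answered, so any stated bias would rest on invented differences. The study is described as descriptive and already stratifies by age, gender and practice.

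**Conclusion.** The point holds as a defect in how the primary outcome is defined. The per-screen wording, combined with a display rule that removes those who have answered, can count returning non-responders more than once. Taken literally, it also counts question-free visits by responders.

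On 80% completion and an assumed 10% of patients returning once, the reported rate lies 1.6 points below the ever-answered rate per screen shown, and about 7 points below it per completed check-in screen. The first figure is an upper value for that r, because it supposes that all returning non-responders see the questions again. The second depends on the literal reading of the Study Summary.

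The 0.01 precision is correct only for a simple random sample of responders. How far clustering widens it cannot be known from the documents; the widths in step 5 are illustrations.

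**What to change.** In the Study Summary, section 6.2 and the SAP:
- Define the primary outcome per unique patient shown the questions, linking check-ins by the unique study identifier.
- Choose first presentation or ever answered in advance, and report the other as a sensitivity result. Ever answered gives frequent attenders more chances; first presentation does not.
- Define response separately for each question, since question 2 may never be displayed.
- State how skip, time-out and partial completion count, and whether skippers are shown the questions again. Sections 3.1, 5.2, 5.3 and 5.4 should then use the same term.
- Give any per-screen rate as secondary, based only on screens that displayed the questions.
- Report 95% confidence intervals that allow for clustering by practice, using a method suited to about 11 clusters, and state that the 0.01 precision in section 6.1 assumes simple random sampling of responders.

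Two additions are optional: the number saying Yes over all patients shown the questions (on the plan's inputs 0.5 × 9604/12005 = 40.0%), and contact and pain percentages standardised to the age, gender and practice mix of those patients. Standardisation corrects only for those three variables.

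The cost is slightly more analysis and wider intervals. No new data item is needed provided that the extract identifies who was shown the questions and carries the same identifier across a patient's check-ins; the day 3 export in section 8.2 is an opportunity to confirm both.
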